1.2 Part 2 Schedule Escalation Segment

The primary objective of the Part 2 schedule escalation segment is to determine the first cycle dose-limiting toxicities (DLTs), maximum tolerated dose (MTD), and a biologically effective and recommended Phase 2 dose regimen (RP2D) of TK216 administered intravenously via continuous infusion through a central venous catheter in patients with relapsed or refractory Ewing sarcoma (ES). (includes patients with Ewing sarcoma family of tumors-ESFT).

Secondary objectives of the dose escalation segment of the study are to assess:

- Safety profile of TK216 alone and combined with vincristine as characterized by Adverse Event (AE) type, severity, timing and relationship to study drug, as well as laboratory abnormalities in the first and subsequent treatment cycles
- Pharmacokinetics (PK) of TK216 in plasma alone and when combined with vincristine

- Antitumor activity of TK216 as measured by Overall Response Rate (ORR), Duration of Response (DOR) as well as Progression-Free Survival (PFS) and Overall Survival (OS)
- Duration of Disease Control defined as first date of disease control identified (either CR, PR or SD) until the date of progression using RECIST, version 1.1
- Pharmacodynamics of TK216

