1.3 Part 3 Expansion Segment

The primary objective of the Part 3 expansion segment is ORR defined as Complete Response (CR) and Partial Response (PR) of the RP2D regimen of TK216 administered intravenously via continuous infusion through a central venous catheter in patients with relapsed or refractory ES. (includes patients with Ewing sarcoma family of tumors-ESFT). The RP2D regimen may include use of vincristine, a standard therapy for Ewing sarcoma.

Secondary objectives of the Expansion Cohort segment of the study are to assess:

- Progression-Free Survival (PFS) defined as time from first dose of TK216 to tumor progression or death due to any cause
- Overall Survival (OS) defined as time from first dose of TK216 to death due to any cause
- Duration of response (DOR) as defined from the first date a response is identified (either CR or PR) until the date of disease progression
- Disease Control (DC) defined as the proportion of patients with a confirmed Complete Response (CR), Partial Response (PR) or Stable Disease (SD)
- Duration of Disease Control defined as first date of disease control identified (either CR, PR or SD) until the date of progression
- Safety and tolerability of TK216 alone and combined with vincristine as characterized by Adverse Event type, severity, timing and relationship to study drug, as well as laboratory abnormalities
- Exploratory biomarker development to enable prediction of drug toxicity, tumor response and the mechanism(s) of acquired study drug resistance.
- Pharmacodynamics of TK216 on molecular targets in surrogate tissue
- Pharmacokinetics (PK) of TK216 alone and when combined with vincristine

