It is anticipated that 4 to 6 cohorts will be completed during the schedule escalation segment of this trial. With the concurrence of the investigators and the study sponsor, further testing may be performed in up to 12 additional patients per dose level to refine the estimation of the MTD and RP2D at intermediate dose levels or to define a higher MTD and RP2D while using Cycle 1 primary supportive care prophylaxis (e.g., with growth factors, antidiarrheals, antiemetics) for bone marrow and/or gastrointestinal toxicities.

The duration of cycles will be variable. Following the scheduled infusions of TK216, a rest period will begin. The next cycle for a patient may begin as soon as all the patient's toxicities attributed to TK216 have resolved to less than Grade 3, or are clinically tolerable Grade 3 toxicities.

Once a patient completes Cycle 2 of any schedule escalation cohort, vincristine can be administered on Day 1 of a subsequent cycle and on Day 1 of each subsequent cycle. The initial dose of vincristine on Day 1 of the starting cycle will be 0.75 mg/m² given via intravenous infusion prior to the initiation of the TK216 infusion. Subsequent doses beginning on Day 1 of the next cycle and beyond will be 1.5 mg/m² up to a maximum dose of 2 mg.

Additional cycles of therapy may be administered provided that the patient meets the following criteria on Day 1 of each cycle:

- ANC \geq 1,000/mm³
- Hemoglobin \geq 8.0 gm/dL (Blood transfusions are permitted.)
- Platelets \geq 50,000/mm³
- Non-hematologic toxicity(s) recovered to less than Grade 3, or are clinically tolerable Grade 3 toxicities
- In patients receiving vincristine, clinically tolerable neurotoxicity, and lack of seizure activity

A rest period of 14 days is required following the first cycle, but the rest period may be reduced following subsequent treatments if the above criteria are met.

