6.3.5.1 Day 1, All Schedule Escalation Cohorts and Cycles (Cohorts 7, 8, 9)

On Day 1 of Cycle 1 for all schedule escalation cohorts, the following procedures will be performed.

- ECOG or Karnofsky/Lansky performance status**;
- Weight**; height Cycle 1 only
- vital signs;
- 12-lead ECG: pre-dose**; For Cycle 1 only, post-dose between 1 and 3 hours after initiation of infusion;
- clinical laboratory tests (hematology, clinical chemistries, coagulation, urinalysis)**;
- for Cycle 1 only, urine pregnancy test (women of childbearing potential only)**;
- complete physical examination**;
- for Cycles 1 and 2 only, pharmacodynamic samples: pre-dose on Day 1; Samples in subsequent cycles may be collected if clinically indicated, for example, to evaluate biomarkers of response
- a single pharmacokinetic sample (see section 6.3.9);
- a single sample for pharmacogenomics to assess CYP polymorphisms
- the TK216 infusion via a central venous catheter will be initiated; infusion will continue for the number of days assigned in the cohort;
- the vincristine infusion will be administered prior to the start of the TK216 infusion starting in cycle 3+ of schedule escalation cohorts, if applicable;
- the vincristine infusion will be administered prior to the start of the TK216 infusion starting in cycle 1 of expansion cohort, if applicable;

- concomitant medication assessment;
- adverse event assessment.

** If the assessments for ECOG or Karnofsky/Lansky performance status, weight, physical examination, ECG, clinical laboratory tests and urine pregnancy test were performed within approximately 72 hours prior to starting a new infusion cycle, these assessments do not need to be repeated.

6.3.5.2 Day 4 (+/-1), All Schedule Escalation Cohorts and Cycles (Cohorts 7, 8, 9)

On Day 4 of Cycle 1, the procedures listed below will be performed.

- continuous infusion via a central venous catheter of study drug;
- For Cycle 1 only, pharmacodynamic sample;
- a single pharmacokinetic sample (see section 6.3.9) if the patient is in the schedule escalation segment;

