6.3.5.9 Pharmacokinetic Assessments, Schedule Escalation Cohorts, Cycle 1 (Cohorts 7, 8, 9)

During Cycle 1 only of the schedule escalation cohorts, PK assessments will be collected at the end of the cycle infusion, +/- 10 minutes, at the following time points:

- 1 hour prior to stopping the infusion;
- immediately prior to stopping the infusion;
- .5 hours (30 minutes) after stopping the infusion;
- 1 hour after stopping the infusion;
- 2 hours after stopping the infusion;
- 4 hours after stopping the infusion;

- and 8 hours after stopping the infusion.

For all cycles during the schedule escalation and expansion cohorts, a single PK assessment will be done at each of the following days, if the scheduled infusion is continuing: Days (+/- 1) 4, 8, 11, 15, 18, and 22.

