8.9 Quality control

The sponsor, or its representative, will be responsible for implementing and maintaining quality assurance and quality control systems with written SOPs to ensure that the study is conducted and data are generated, documented (recorded), and reported in compliance with the protocol, cGCP and the applicable regulatory requirements.

9 Statistical Considerations

The clinical outcomes, laboratory, PK, and other safety data from all segments of the study will be analyzed descriptively. In addition to determining DLT and RP2D, results will be analyzed to

determine if a sufficient response signal and safety profile justifies further study. Descriptive statistical summaries for demographic and patient baseline characteristics will be produced, as well as statistical summaries of safety, efficacy and pharmacokinetic/pharmacodynamic results, where categories for statistical summaries will consist of the dose level and duration initially assigned for Parts 1 and 2 dose and schedule escalation, and the initial dose and duration in the Expansion Cohort (RP2D). In addition, exploratory analyses of both toxicity, response (ORR), Stable Disease (SD) and pharmacodynamic data will be performed for both the assigned and actual daily dose and duration of infusions, the actual number of days of treatment, and for cumulative exposure to study drug as expressed by the product sum of dose over time (area under the dose-time curve).

Disease Control Rate (DCR) defined as the proportion of patients with a confirmed Complete Response (CR), Partial Response (PR) or Stable Disease (SD) per RECIST v1.1 Duration of Response (DOR) defined from the first date a response is identified (either CR or PR) until the date of objective tumor progression per RECIST v1.1 Progression-Free Survival (PFS) defined as time from first dose of TK216 to objective tumor progression per RECIST v1.1 or death due to any cause, whichever occurs first.

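### Parts 2 and 3 have safety and PK objectives for TK216 with and without vincristine, but no planned summary uses vincristine status

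*Combined protocol and SAP*

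**What the plan says.** **Objectives.** Section 1.2 (Part 2) lists "Safety profile of TK216 alone and combined with vincristine as characterized by Adverse Event (AE) type", with a matching PK objective. Section 1.3 (Part 3) lists "Safety and tolerability of TK216 alone and combined with vincristine", again with a matching PK objective.

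**Vincristine in Part 2.** Under Section 2.3, once a patient has finished Cycle 2, "vincristine can be administered on Day 1 of a subsequent cycle". It is optional.

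**Vincristine in Part 3.** Section 2.4 gives it to the first three patients on Day 1 of each cycle, to three more if one of the three has a DLT, and to the remainder if a DLT condition is met. With two or more DLTs in the first six, dosing of one or both drugs is revised. Section 6.3.5.1 says "the vincristine infusion will be administered prior to the start of the TK216 infusion starting in cycle 1 of expansion cohort", but that sentence ends with a proviso limiting it to where it applies. Section 1.3 also treats vincristine as an optional part of the RP2D regimen.

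**Analysis.** Section 9 groups summaries of safety, efficacy and PK/PD by "the dose level and duration initially assigned for Parts 1 and 2 dose and schedule escalation", and by initial dose and duration for the expansion cohort. It adds exploratory analyses by assigned and actual dose and duration, days treated and cumulative exposure. Adverse events are shown by dose group (Sections 9.4 and 10.3) and PK by dose level, or by dose group and time point (Sections 9.5 and 10.4). Response is also pooled over everyone at the RP2D across phases (Section 9.7).

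**The concern.** Four stated secondary objectives (safety and PK, in Parts 2 and 3) call for a comparison, or at least a separation, that no planned table makes. A Part 2 patient who adds vincristine in Cycle 3 is still summarised under the TK216 dose and duration assigned at entry. Toxicity and response seen on the combination are then displayed as belonging to a TK216 dose group. Attribution does not clearly solve this. Section 4.1.7.1 grades relationship to study drug, Section 7 describes both agents under the heading of study drugs, and no separate vincristine attribution is planned.

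The RP2D pool in Section 9.7 adds a second mixture: Part 2 patients with no vincristine before Cycle 3, and Part 3 patients who are meant to have it from Cycle 1. At stake is whether a reader of the final tables can tell what TK216 does by itself from what the combination does.

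**Working it through.** The point is mainly textual. The only arithmetic concerns how firm the planned Part 3 path is.

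1. **Is vincristine a category anywhere?** Going through Sections 9, 9.4 to 9.7, 10 and 10.3 to 10.6, the grouping variables are initial dose and duration, actual dose and duration, days treated, cumulative exposure, dose group, dose level, time point, all RP2D patients, and all dose groups combined. Vincristine appears in none.

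2. **When are Part 2 data free of vincristine?** Section 2.3 makes Cycles 1 and 2 TK216 alone by rule. From Cycle 3 the data may be mixed, within and between patients.

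3. **Which Part 2 responses are certain to precede vincristine?** Section 4.1.6.6 places scans in even-numbered cycles. If vincristine starts in Cycle 3, the only post-baseline scan before it is in Cycle 2; the next is in Cycle 4.

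4. **What PK is available?** Section 6.3.5.9 states "For all cycles during the schedule escalation and expansion cohorts, a single PK assessment will be done" on listed days while the infusion continues, so single samples exist with and without vincristine. The serial end-of-infusion profile is taken in Cycle 1 only, which in Part 2 is TK216 alone.

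5. **How certain is vincristine for all of Part 3?** The documents give no DLT rate for the combination, so I assume a true rate p of 0.1, 0.2 or 0.3, with q = 1 − p. I also assume that 0 of 3 leads on to vincristine for the rest, which Section 2.4 implies but does not state.
   - No DLT in the first three: q³ = 0.73, 0.51, 0.34.
   - One of three, then none of the next three (exactly 1 of 6): 3pq² × q³ = 0.18, 0.20, 0.15.
   - Two or more DLTs, so dosing is revised: 1 − q³ − 3pq² × q³ = 0.09, 0.29, 0.51.

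   For p = 0.2: q³ = 0.512; 3 × 0.2 × 0.64 × 0.512 = 0.197; 1 − 0.512 − 0.197 = 0.291.

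   The middle branch has no rule. Section 2.4 continues when fewer than 1 of 6 have a DLT and revises at two or more, so exactly 1 of 6 falls between them. Vincristine from Cycle 1 for all of the roughly 18 patients is therefore the intended path, not a certainty.

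6. **Are the primary Part 2 decisions touched?** No. DLT and MTD rest on Cycle 1, and vincristine cannot start before Cycle 3.

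**The case against.** The strongest reply is that the data already allow an answer and the plan partly gives one. Part 2 Cycles 1 and 2, Part 1, and Part 4 before any vincristine are all TK216 alone. Laboratory data are summarised at each time point and PK by dose group and time point, so the early Part 2 time points are already vincristine-free. Adverse events are also shown by relationship to study drug, and all raw data are listed. This stands as far as it goes: a pre-specified display is missing, not the information. It does not supply the combination side, separate adverse events by vincristine status, or unpick the RP2D pool.

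Three stronger readings are tempting, and the documents do not support them.

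- A reader might infer that the objectives cannot be answered at all. The vincristine-free Part 2 cycles and the all-cycle PK samples show that they can be, in part.
- A reader might infer that every Part 3 patient receives vincristine from Cycle 1. Sections 1.3, 2.4 and 6.3.5.1 make that conditional.
- A reader might infer that single-agent response rate is a promised Part 2 result. The antitumor objective in Section 1.2 makes no distinction by vincristine; only the safety and PK objectives do.

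Nor should cohort size be read as an effect size. One event among 3 or 6 patients is 33 or 17 percentage points (1/3, 1/6), but that says nothing about how much vincristine contributes.

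**Conclusion.** The gap is real and moderate. The stated grouping rule mixes vincristine-free and vincristine-exposed data, and four secondary objectives have no matching analysis. On the planned path Part 3 supplies no TK216-alone group of its own. With assumed DLT rates of 0.1 to 0.3, the branch in which dosing is revised has probability 0.09 to 0.51, so that statement holds only for the planned path. The size of any distortion cannot be computed, because the documents give neither the uptake of vincristine in Part 2 nor its effect. The consequence is confined to descriptive secondary summaries. The first-cycle DLT and MTD decisions and the sample sizes are unaffected.

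**What to change.** 1. Add vincristine status as a summary category for adverse events, laboratory data and PK. In Part 2 make it time-varying: before, and from, the first vincristine dose, with the patients and cycles in each period shown. Show the Section 9.7 RP2D pool by vincristine exposure as well.
2. Keep best response as Section 9.7 defines it. Add a supplementary count of responses first seen before vincristine, and say that it may rest on the Cycle 2 scan alone.
3. Compare single-sample TK216 levels within patient between cycles without and with vincristine, descriptively and at the same TK216 dose. State the limits: vincristine is optional; its use is confounded with cycle number and with the dose or duration changes that Section 2.3 allows; only patients who reach Cycle 3 contribute; and serial end-of-infusion PK exists in Cycle 1 only.
4. Name Part 2 Cycles 1 and 2 as the TK216-alone reference for Part 3, or remove the TK216-alone element from the Part 3 objectives.
5. Reconcile Sections 1.3, 2.4 and 6.3.5.1 on when Part 3 patients receive vincristine, including the case of exactly 1 DLT in 6. Which rule applies is for the clinical team.

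The cost is revised analysis wording and a few extra tables with small counts. No new data are needed and no sample size changes.

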1.4 Part 4: Dose and Schedule Evaluation Segment

Primary Objective:

The primary objective of the Part 4 dose and schedule evaluations segment is to assess ORR defined as Complete Response (CR) and Partial Response (PR), per RECIST v1.1, at a starting dose of 175 mg/m²/day of TK216 administered intravenously via continuous infusion over 28-days in patients with relapsed or refractory Ewing Sarcoma.

Secondary Objectives:

- Duration of response (DOR) per RECIST v1.1
- Disease control rate (DCR) per RECIST v1.1
- Progression free survival (PFS) per RECIST v1.1
- Overall survival (OS)
- Safety and tolerability of TK216 alone as characterized by AE type, severity, timing and relationship to study drug, as well as laboratory abnormalities

- Pharmacodynamics of TK216; Exploratory biomarker development to enable prediction of drug toxicity, tumor response and the mechanism(s) of acquired study drug resistance
- Pharmacokinetics of TK216 alone

2. Study Design

TK216-01 is a multicenter, open-label, Phase 1/2 study in which the safety and efficacy of TK216 will be evaluated in patients with relapsed or refractory ES (including patients with ESFT).

Once an appropriate patient has been identified, a 30-day screening period will begin to evaluate eligibility using the defined study inclusion and exclusion criteria.

The study will be executed in several Parts:

- **Part 1:** Dose Escalation Segment (Cohorts 1-6)
- **Part 2:** Schedule Escalation Segment (Cohorts 7-9)
- **Part 3:** Expansion Segment (Cohort 10)
- **Part 4:** Dose and Schedule Evaluation Segment (Cohort 11)

All patients will be treated until objective tumor progression per RECIST v1.1., withdrawal of consent, unacceptable toxicity, study termination by sponsor, or a maximum of 2-years. Patients may receive supportive care for bone marrow and/or gastrointestinal adverse events (e.g., with growth factors, antidiarrheals, antiemetics) and prophylaxis for established toxicities that are recurrent.

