It is anticipated that 6 to 8 cohorts will be completed during the dose escalation segment of this trial. With the concurrence of the investigators and the study sponsor, further testing may be performed in up to 12 additional patients per dose level to refine the estimation of the MTD and RP2D at intermediate dose levels or to define a higher MTD and RP2D while using Cycle 1 primary supportive care prophylaxis (e.g., with growth factors, antidiarrheals, antiemetics) for bone marrow and/or gastrointestinal toxicities.

Additional cycles of therapy may be administered provided that the patient meets the following criteria on Day 1 of each cycle:

- ANC \geq 1,000/mm³
- Hemoglobin \geq 8.0 gm/dL (Blood transfusions are permitted.)
- Platelets \geq 50,000/mm³
- Non-hematologic toxicity recovered to \leq Grade 1 (or tolerable Grade 2)

Intra-patient dose escalation will be permitted during the dose escalation segment of this trial. Patients may have their dose of TK216 increased after they have completed 2 cycles of treatment at their assigned dose, assuming their initial dose was well tolerated and the subsequent cohort (at the next higher dose level) has been well tolerated through Cycle 1. At the investigator's discretion, the dose escalation can either take the form of an increase in daily dose with 7 days of dosing and 14 days of rest, or an increase of duration, with 14 days of dosing and 7 days of rest, but not both.

Other schedules of administration may be investigated after tolerability and PK data are acquired with this schedule.

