If TK216 treatment has been well tolerated in Cycle 1 and 2, starting in Cycle 3 the duration of the TK216 infusion may be increased (e.g. from 14 to 17 or 14 to 21 days). If the longer infusion is well tolerated, the duration of the TK216 infusion may be increased further in subsequent cycles. There is no maximum treatment duration. If a longer infusion time is not well tolerated, the patient may remain on study, but receive a shorter duration of TK216 infusion in the next treatment cycle. The assessments noted for Days 8+/-1 and 15+/-1 in the Section 16.3 Schedule of Events (Schedule Escalation and Expansion Cohorts) should be performed every 7-8 days during longer infusions (Adverse events, Concomitant medications, Vital signs, Symptom driven physical exam, Hematology, Clinical chemistry, Coagulation, Urinalysis, and Plasma for PK assessment). A complete blood count (CBC with differential) should be obtained approximately half way between the weekly assessment at the study center or local laboratory.

Patients may have their dose increased to the next dose level at the next cycle if any cycle of TK216 is

well-tolerated with no clinically significant toxicity greater than Grade 2 attributed to TK216. If TK216 treatment has been well tolerated in Cycle 1 and 2, starting in Cycle 3 the duration of the TK216 infusion may be increased, in consultation with the Sponsor.

Intra-patient dose increases will be permitted during the schedule escalation segment of this trial. If any cycle of TK216 is well tolerated with no clinically significant toxicity greater than Grade 2 attributed to TK216, then the daily dose of TK216 may be increased to the next dose level on the next cycle upon discussion with the sponsor. No cycle should initiate:

1. Both vincristine for the first time and have a dose increase, or
2. Both vincristine for the first time and have an increase in the length of TK216 infusion, or
3. Increase the length of infusion for the first time and have a dose increase.

After the RP2D has been determined (recommended dose and schedule), an expansion cohort will be enrolled.

Table 2 Dose Limiting Toxicity – Part 2 Schedule Escalation Segment

Category	Criteria

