2.6.3 Dose Increase (Part 4)

The Cohort 11 starting dose is 175 mg/m²/day for 28 days. If the patient's response is inadequate after at least one post-baseline assessment and they are not experiencing toxicities at this dose level, the Investigator may increase the dose to 200 mg/m²/day after discussion with the Sponsor.

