9.7 Efficacy

A modified intent to treat (mITT) approach will be used for efficacy analysis, in which the mITT population will consist of all patients who receive at least a partial dose of study therapy (i.e., any portion of the continuous infusion). Tumor response rates will be summarized by dose group and for all patients who receive the RP2D, including those from the dose and schedule escalation and expansion phases. Responses will be classified as CR, PR, SD or PD according to RECISTv.1.1 criteria. Summaries will be based on the best response recorded up until disease progression. Patients who discontinue prior to the first protocol-scheduled response assessment post first infusion will be considered as non-responders in the primary efficacy analysis. Objective tumor response (CR or PR) will also be summarized, as will PFS, OS, DCR and duration of response and DCR. Time to event data will be summarized by Kaplan-Meier methods, including 25th, 50th (median) and 75th percentiles with point estimates and two-sided 95% confidence intervals, as well as number and percent of censored observations.

10 Statistical analysis

The statistical analyses will be reported using summary tables, figures, and data listings. Continuous variables will be summarized with means, standard deviations, medians, minimums, and maximums. Categorical variables will be summarized by counts and by percentage of patients in corresponding categories. All raw data obtained from the case report forms as well as any derived data will be included in data listings. All analyses will be based on the Safety Population, which will include all patients who receive any amount of study drug.

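### The exploratory analyses by total treatment days and cumulative dose use an exposure that the outcome itself sets, so even an inactive drug would show a false relation with stable disease

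*Combined protocol and SAP*

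**What the plan says.** The opening of Section 9 says that "exploratory analyses of both toxicity, response (ORR), Stable Disease (SD) and pharmacodynamic data will be performed for both the assigned and actual daily dose" and the infusion durations. The same sentence adds two further exposure measures: "the actual number of days of treatment, and for cumulative exposure to study drug as expressed by the product sum of dose over time". No exposure window is given there or in the efficacy and safety text of Sections 9.4, 9.7, 10.3 and 10.6.

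Other sections determine how long and how intensively a patient is treated:

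- **Stopping.** Section 2: "All patients will be treated until objective tumor progression per RECIST v1.1., withdrawal of consent, unacceptable toxicity", sponsor termination, or two years.
- **Outcome.** Section 9.7: "Summaries will be based on the best response recorded up until disease progression".
- **Increases, Parts 1-3.** Section 2.2: "Patients may have their dose of TK216 increased after they have completed 2 cycles of treatment at their assigned dose". Section 2.3: "If TK216 treatment has been well tolerated in Cycle 1 and 2, starting in Cycle 3 the duration of the TK216 infusion may be increased"; Section 2.4 repeats this for the expansion cohort. In Part 2 the daily dose may also rise after any well-tolerated cycle.
- **Reductions.** Sections 2.6.1 and 2.6.2 hold or lower the dose for toxicity.
- **Increase, Part 4.** Section 2.6.3 allows a rise "If the patient's response is inadequate after at least one post-baseline assessment and they are not experiencing toxicities at this dose level".

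The main summaries in Section 9 are by the dose and duration initially assigned.

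**The concern.** An exposure-response analysis is informative only if exposure is fixed before the outcome. Here a patient with progression at the first scan normally stops, while a patient with stable disease or a response continues and accumulates days and dose. Long exposure then marks a good outcome whether or not the drug works.

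Overall actual daily dose is also affected. In Parts 1-3 higher doses and longer infusions go to patients who stayed on and tolerated treatment. In Part 4 a higher dose can follow a poor response, which pushes the other way. Toxicity lowers later exposure, while longer treatment gives more time for an event to occur.

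The practical risk is misreading. Infusion length is an active question across the parts, and the Part 3 rule in Section 9.3 counts stable disease of at least 3 months. A table showing more treatment days among patients with stable disease could be taken as evidence of activity or as support for longer infusion.

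**Working it through.** **Plan figures.** The exposure analyses carry no stated figure. The nearest ones are the rules in Section 9.3. Using P(X ≥ 4) = 1 − Σ(k=0..3) C(n,k) p^k (1−p)^(n−k):

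- Part 4, n = 21: 0.0189 at 5% and 0.808 at 25% (stated: one-sided 0.025 and 80%).
- Part 3, n = 18: 0.098 at 10% and 0.835 at 30% (stated: 0.10 and 80%).

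Both rules hold as stated, and both are counts of patients with no exposure term.

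**The mechanism by hand**, with no interruptions or dose changes and treatment to the scan that shows progression:

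- Part 4 has continuous 28-day cycles and scans about every 8 weeks (56 days). Progression at the first scan gives 56 days and 56 × 175 = 9,800 mg/m². Stable disease at the first scan and progression at the second gives 112 days and 112 × 175 = 19,600 mg/m². The two groups cannot overlap.
- Part 1 has 7 infusion days per 21-day cycle and scans every 6 weeks, so 14 infusion days to the first scan and 28 to the second. Days again cannot overlap. Cumulative dose can: 28 × 18 = 504 mg/m² for a patient at 18 mg/m²/day who progresses at the second scan, and 14 × 36 = 504 mg/m² for a patient at double that dose who progresses at the first. Pooling dose levels therefore weakens the artefact for cumulative dose without removing it.

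An inactive drug still yields enough stable disease for this to show. With exponential time to progression, the share progression-free at day 56 is 2^(−56/median). For assumed medians of 1.5 and 4 months (30.4 days each) this is 2^(−56/45.6) = 0.43 and 2^(−56/121.6) = 0.73, or about 9 to 15 of 21 patients.

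**Simulation of an inactive drug.** The treat-to-progression rule, two-year cap, scan intervals and Part 4 sample size come from the documents. The following are assumptions: median time to progression 1.5 to 4 months, unrelated to dose; a 5% chance of a response call at each scan without progression; 1% withdrawal per month; adverse-event rate 0.1 or 0.3 per month; and, for pooled Part 1, 27 patients at 18-216 mg/m²/day. AUC is the chance that a patient with the outcome has more exposure than one without (0.5 = no relation). The two-sided Mann-Whitney test is a yardstick and is not in the plan.

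| Outcome and exposure | Setting | AUC | p<0.05 |
|---|---|---|---|
| Disease control, days | Part 4 and pooled Part 1 | 1.00 | 99-100% |
| Disease control, cumulative dose | Part 4 | 1.00 | 99-100% |
| Disease control, cumulative dose | Pooled Part 1 | 0.77-0.84 | 71-78% |
| Response, days | Part 4 | 0.81-0.86 | 15-26%* |
| Response, days | Pooled Part 1 | 0.81-0.84 | 26-47%* |
| Response, cumulative dose | Part 4 | 0.80-0.86 | |
| Response, cumulative dose | Pooled Part 1 | 0.70-0.71 | |

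*Among trials with at least one responder. In Part 4, 9-49% of trials had none.

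**Toxicity against days, Part 4.** AUC is 0.63-0.73 if adverse events never stop treatment, 0.48-0.51 if half the patients would stop at an event, and 0.28-0.35 if all would.

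**Same drug, exposure not set by the outcome.** Daily dose drawn independently of outcome (standing in for assigned dose) against disease control: AUC 0.50-0.51, p<0.05 in 4-6%. Cumulative dose to the first scan against response, in patients still on treatment then: AUC 0.50-0.51, p<0.05 in 2-5%. The false relation disappears.

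**The case against.** Section 9 calls the data analysis descriptive and these analyses exploratory, and it specifies no test for them. Its main summaries use assigned dose and duration, and the criticised sentence includes assigned dose too, so part of the remedy is already planned. All of this stands. It limits the consequence but does not cure the bias: an exploratory label guards against over-reading chance findings, not against a relation built into the comparison.

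Four stronger readings are tempting, and the documents do not support them:

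- **That an inactive drug will always show a strong relation with response.** It yields few responders, or none, so the bias is large in size but often cannot be detected at 21 to 27 patients.
- **That toxicity is biased upward through time at risk.** That holds only if events do not feed back on treatment. Sections 2 and 2.6 stop, hold or reduce treatment for toxicity, so the direction is open.
- **That the decision on further study rests on these analyses.** The sentence in Section 9 about justifying further study refers to results in general, and the rules in Section 9.3 use patient counts only. Schedule steps in Section 2.3 follow first-cycle results.
- **That separation in Part 4 is always complete.** Section 2.5 and the heading of Section 4.2.6 contemplate TK216 after progression, which loosens the link, so AUC 1.00 is an upper case there.

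**Conclusion.** The concern holds in a limited form. Analyses by total treatment days or total cumulative dose would mislead if carried out as written.

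- **Stable disease or disease control:** the false relation is nearly automatic for days. For cumulative dose pooled over dose levels it is strong (AUC 0.77-0.84).
- **Response:** the bias is positive but often undetectable.
- **Toxicity:** the bias is of unknown direction, so the result could not be interpreted.

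Overall actual daily dose shares the problem by reasoning from the dose-change rules; its size was not simulated. The disease-control result held across the assumed medians of 1.5 to 4 months. The cumulative-dose figures also depend on the assumed dose mix. The summaries by assigned dose and duration and the decision rules in Section 9.3 are unaffected.

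**What to change.** Amend the exploratory-analysis sentence in Section 9 as follows:

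1. **Response and stable disease.** Rest inference on the assigned dose and duration already planned, plus actual exposure up to a fixed landmark (end of Cycle 1 or the first scheduled scan), in patients still on treatment and without the outcome at that point. Because stable disease can be scored at the first scan itself, the Cycle 1 landmark is the one to use for it.
2. **Toxicity.** Use Cycle 1 exposure, or a time-to-first-event model with exposure up to each time point, and report events per treated time. For events within Cycle 1, assigned dose or the time-varying model is safer, since an event can cut short that cycle's exposure.
3. **Total treatment days, total cumulative dose and overall actual daily dose.** Report these as description only, and say that they depend on outcome.

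The cost is analysis wording: under Section 7.4, doses given and interruptions are already recorded in the eCRF, and no treatment rule changes. Landmark analyses drop patients who progress before the landmark. Within Part 4 every patient starts at the same dose, so assigned dose offers no contrast there and early exposure will vary little; the revised analysis will be less informative in that part, and the report should say so.
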